**Actigraphic Sleep Measurement:**

Daily sleep, activity, and light exposure will be collected via the Resironics Actiwatch. This actigraphic wrist-watch device uses a built-in accelerometer to measure and record ambulatory

**FORM: Application for Human Research**

NUMBER	FORM DATE	PAGE
F200	02/2014	27 of 39

activity levels and sleep 24 hours a day. This data can then be analyzed via sleep analysis software (Actiware 5®) that includes algorithms that transform activity data into probable sleep periods. The Actiwatch also includes three color light sensors that provide irradiance and luminous lux recordings in three color bands of the visible spectrum, including red, green, and blue. The light sensor will be used to verify that subjects are in fact undergoing the daily light treatment and will permit covariation of other daily light sources in the statistical analyses. The device also records periods of off-wrist time to determine compliance. Data will be downloaded using the Actiwatch-2 communication dock after week 7 of the study.

Participants will also keep a daily sleep log during the 7-week period.

**Optional Sleep Follow-up Monitoring:**

Subjects may choose to participate in an additional 6 weeks of sleep monitoring. Willing subjects who indicate their agreement on the consent document will continue wearing the wrist-worn actigraph and complete daily sleep diaries for up to 6 weeks after termination of the light exposure period.

**Follow-Up:** One year post-participation in the study, subjects who consent will have a follow-up phone call where they will be administered the RPCSQ, the PHQ9, and be asked about general sleep problems using the ESS.

**Healthy Control/Effect Localization Arm:**

Following the initial assessment, subjects will have a saliva sample collected via a small plastic tube placed in the lower part of their mouth. This is being done to measure melatonin levels and is not painful. Once subject eligibility has been determined, they will be fitted with a heart rate monitor that has 2 leads to attach to the chest which will be worn for the duration of the visit, save the MRI scanner. They will complete study assessments and then subjects will have electrodes attached for EEG (electroencephalography) recordings during their light exposure period. This is being done to measure changes in beta, alpha and theta over the light exposure period and only takes a few minutes to attach the EEG headset. Subjects will sit in a dark room while being exposed to 30 minutes of amber (placebo) light. For 10 minutes of this time, subjects will be asked to sit quietly, and fixate on a cross on the opposite wall. After this time, these subjects will be exposed to either blue wavelength light per the goLITE BLU, or they will be exposed to amber wavelength placebo/sham light for 30 minutes. They will be asked to repeat the cross fixation for another 10 minutes during the light exposure period (amber/blue) in order to help get clean EEG data. Total light exposure time will be 60 minutes. Once this is complete, another saliva sample will be collected. Subjects will then undergo an MRI scanning session. A third saliva sample will then be collected. Following this, subjects will be given an Actiwatch and instructed in its use to wear until their follow-up appointment for around 8:30pm the same day.

While wearing the EKG device, a final melatonin sample will be collected at this follow-up appointment and the Actiwatch will be collected. This follow-up visit saliva sample is being performed to measure the difference in melatonin levels for subjects who received the active versus sham light exposure during their initial visit. Melatonin levels should be higher later at night as levels

**FORM: Application for Human Research**

NUMBER	FORM DATE	PAGE
F200	02/2014	28 of 39

stay flat during the day and increase exponentially in the evening just prior to when subjects are predisposed to sleep.

All saliva samples will be stored in protected access freezers in CaTS until they are processed and analyzed. Analysis will be done in the UACC lab by our study team per the Melatonin Assay Protocol. Transport will occur the day of analysis in a sealed Styrofoam container from CaTS storage directly to the lab by study personnel.

**Post-Treatment Assessment and Scan:**

At the completion of 6-weeks of MBLT or SPLT, participants will return to the laboratory and turn in the light device. Participants will undergo a comprehensive neurocognitive assessment virtually identical to the pre-treatment assessment. A series of functional and structural neuroimaging scans will be repeated to evaluate the impact of treatment on brain function and structure. Finally, in order to provide an objective measure of sleep latency, an MSLT with polysomnography will be performed at the same time of day as during the first visit.

**Healthy Control/Effect Localization Arm:**

Following exposure to the blue or amber wavelength light, participants will undergo a comprehensive neurocognitive assessment akin to the pre-treatment assessment. A series of functional and structural neuroimaging scans will be repeated to evaluate the impact of treatment on brain function and structure.

**I. BIOSTATISTICAL ANALYSIS**

Several global outcomes and their interpretations include:

- 1) “If the effects of MBLT versus SPLT are not different and improvement is observed in both groups”—this would suggest that nonspecific effects (practice, maturation, recovery) occurred but were unrelated to the MBLT treatment. Thus there is no specific benefit to the use of MBLT versus placebo. Based on such an outcome, there would be no recommendation for the use of MBLT for treatment of post-concussive symptoms. Secondary analyses correlating cognitive/symptom improvement with changes in brain structure and function may identify new avenues of research and would still contribute valuable knowledge regarding these relationships.
- 2) “If effects of MBLT versus SPLT are not different and no significant improvement is observed in either group”—this finding is less likely, as continued improvement between the two sessions would be expected due to gradual recovery during the first year and due to practice effects associated with repeated assessment. While such a finding would clearly suggest that there is no specific benefit to the use of MBLT versus placebo, it would raise suspicion that the assessments were invalid or insensitive.
- 3) “If MBLT is better than SPLT”—this is the hypothesized effect. This would support the hypothesis that MBLT is beneficial in the treatment of post-concussive symptoms relative to placebo. Regression analysis between the change in symptoms/neurocognitive function and measures of sleep and mood would identify whether this was due to sleep related changes or whether the changes were due to the mood altering effects of MBLT, or both. Similarly, changes in one condition and not the other will also be examined for their relationship to

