#### **5) Study Population**

##### **Main Study Arm:**

**FORM: Application for Human Research**

NUMBER	FORM DATE	PAGE
F200	02/2014	14 of 39

Forty (40) individuals between the ages of 18 and 50 with a documented history of a “concussion” or mTBI in the preceding 18 months but no sooner than 4 weeks prior to the screening will be recruited to participate in the main study arm. It is anticipated that approximately 6 participants (i.e., 17%) will withdraw early or fail to comply with procedures. Thus, a total of 40 participants will be run to achieve a total sample size of 30 complete datasets. The occurrence of a concussion or mTBI must be documented by a medical/objective professional (e.g., sports trainer, coach, physician, nurse, etc.) report. In addition, at least half of the participants recruited for each condition will be required to have complaints consistent with sleep onset insomnia (i.e., trouble falling asleep) as measured by Insomnia Severity Index (ISI) or delayed sleep phase disorder (i.e., not feeling sleepy at bedtime and/or not able to fall asleep until much later than bedtime). Participants with a lifetime history of head injury leading to loss of consciousness greater than 30 minutes will be excluded. Other exclusion criteria will include any current medical condition that would be contraindicated for scanning, other known neuropathology (e.g., tumor, neurodegenerative disease, normal pressure hydrocephalus, etc.), abnormal visual acuity that is not corrected by contact lenses, metal within the body, or time since injury exceeding 18 months.

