## 7) Procedures involved in the Human Research

Please note: The Human Research Protection Office (HRPO) with US Army Medical Research and Materiel Command must approve any major amendment to this study prior to its implementation. Therefore, implementation of any amendment which requires HRPO approval, including use of revised consents, will not begin until HRPO approval is received.

This study will be conducted over a 3-year period. All main study arm participants will undergo an initial assessment and two testing/scanning sessions separated by 6-weeks of treatment with blue light or a sham placebo amber light treatment. Healthy control subjects will undergo an initial assessment and a single testing/scanning session only and their participation will be complete. Ten to 16 subjects will be run each year (i.e., 2 sessions per subject = 20-32 scan/assessment sessions per year). Data collection will continue for an additional 6 weeks after completion of light therapy for subjects who elect to participate in this optional research. Potential subjects will learn about the study through posted flyers, internet and radio advertisements, and physician referrals. Interested participants will call the pre-specified telephone number and will be given a brief introduction to the study and be informed about the exclusionary criteria and requirements of the study.

Before enrollment, interested participants will be required to contact their physician/medical provider/other professional witness (e.g., sports trainer, coach) to have documentation of head injury/concussion and severity provided. Participants meeting inclusion criteria will provide informed

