whether to use the light immediately upon arising, or after morning hygiene, meals, drive, etc., but will still ensure that all treatment occur in the morning hours. The instrument is equipped with a timer to ensure 30 minutes of exposure. Appropriate use will involve placing the light device at a distance between 12-24 inches, offset from center to reduce glare. Participants will be instructed not to look directly at the light source, but to allow the light to enter from their peripheral vision. Each morning, within 2 hours of arising from sleep, participants will 1) document the time, indicate sleepiness using the Stanford Sleepiness Scale (SSS), activate the light device, and document the sleep and wake times from the previous day. At the completion of the light period, participants will again indicate sleepiness using the SSS. To further monitor compliance, the wrist actigraph will also include a light monitor. Participants will be instructed to ensure that the light sensor of the actigraph is exposed to the light source for the full 30-minute duration in order to verify compliance. This will permit cross-verification that subjects have in fact used the blue wavelength light at the specified times (and will allow co-variation for additional light effects in statistical analyses). MBLT exposure will be conducted daily for 6-weeks for all participants. Participants will also be contacted weekly by phone to ensure compliance, answer questions, and collect a weekly Epworth Sleepiness Scale.

Half of the participants will be randomly assigned to the morning MBLT or a sham placebo light treatment (SPLT). Participants in the MBLT group will be administered blue light therapy using the standard goLITE BLU device, whereas participants in the SPLT group will be given identical appearing goLITE devices where the standard bright blue-wavelength LEDs have been replaced with amber LEDs. The goLITE BLU has been shown to have a narrow bandwidth, peaking at  $\lambda = 469$  nm, at 214 Lux, and panel irradiance  $\text{mW/cm}^2 = 1.23$  at 20 cm. A similar appearing amber LED system (goLITE AMBER) will be employed for the SPLT devices, but will peak at  $\lambda = 566$  nm, at 180 Lux, and total irradiance  $(\text{mW/cm}^2) = 0.58$ .

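### A null comparison is to be read as no specific benefit, with no confidence interval, margin or inconclusive outcome, at about 15 completers per arm

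*Combined protocol and SAP*

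**What the plan says.** Section 3, item 7, I. Biostatistical Analysis, lists four possible global outcomes and an interpretation of each. Two are nulls.

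- **Outcome 1** (arms do not differ, both improve). The improvement is put down to nonspecific effects, and the text continues: "Thus there is no specific benefit to the use of MBLT versus placebo". It then says: "Based on such an outcome, there would be no recommendation for the use of MBLT for treatment of post-concussive symptoms".
- **Outcome 2** (arms do not differ, neither improves). The plan thinks this less likely, but says it would "clearly suggest that there is no specific benefit to the use of MBLT versus placebo". It adds one caveat: "it would raise suspicion that the assessments were invalid or insensitive".

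Outcomes 3 and 4 cover MBLT better and SPLT better. No outcome is labelled inconclusive. The document supplied states no confidence interval, margin, smallest important difference, alpha, power or effect size for the comparison.

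Item 5, Study Population, enrols 40 in the main arm to reach a "total sample size of 30 complete datasets". The subsection Six-Week Light Exposure Treatment in item 7 assigns half of the participants to each device.

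**The concern.** A non-significant difference supports a claim of no benefit only if the data also rule out a benefit worth having. The usual evidence is a confidence interval that lies below a stated margin. The plan goes from no detected difference to no specific benefit without that step. With about 15 completers per arm, the same non-significant result can arise from no effect or from a moderate one.

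The Background says that no published study has examined this kind of light therapy for outcome in mTBI. A report of no specific benefit from an early small trial could discourage further work even though its data left the question open.

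**Working it through.** **Inputs from the document.** 40 enrolled, 30 complete datasets, equal allocation, so 30/2 = 15 per arm.

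**The plan's own sample-size figure.** Item 5 expects that "approximately 6 participants (i.e., 17%) will withdraw early or fail to comply with procedures".
- 30/(1 − 0.17) = 36.1, so 37 would be enrolled, not 40.
- 6/36 = 16.7% matches the percentage but implies 36 enrolled.
- Going from 40 to 30 is a loss of 10/40 = 25%.
- Losing 6 of 40 leaves 34, or 17 per arm.

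The stated figures do not agree with each other. I therefore carried 15, 17 and 20 per arm (20 being no loss at all).

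**Assumptions, not in the document.** One endpoint; two-sided 5% test; effects in SD units; either unadjusted, or adjusted for baseline with correlation r = 0.7. The 0.5 and 0.8 SD effects and margins are illustrative.

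**Precision.** Half-width of the 95% interval = t(0.975, df) × √(2/n) × √(1 − r²), with df = 2n − 2 unadjusted and 2n − 3 adjusted. At n = 15:
- unadjusted: 2.048 × 0.365 = 0.75 SD
- adjusted: 2.052 × 0.365 × 0.714 = 0.54 SD

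An observed difference of exactly zero would still be compatible with a benefit of that size.

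**Chance of missing a real benefit.** This is one minus power from the non-central t distribution, with non-centrality d × √(n/2)/√(1 − r²). At n = 15 and d = 0.5 the non-centrality is 1.37 unadjusted (power 0.262) and 1.92 adjusted (power 0.456).

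| Per arm | Half-width, SD (unadj. / adj.) | 0.5 SD missed (unadj. / adj.) |
|---|---|---|
| 15 | 0.75 / 0.54 | 74% / 54% |
| 17 | 0.70 / 0.50 | 71% / 49% |
| 20 | 0.64 / 0.46 | 66% / 42% |

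At 15 per arm a true 0.8 SD benefit is missed 44% (unadjusted) or 16% (adjusted) of the time.

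**If the true difference is zero.** Simulation at 15 per arm, counting non-significant results whose upper 95% limit still reaches the margin:

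| Margin | Unadjusted | Adjusted |
|---|---|---|
| 0.5 SD | 75% | 55% |
| 0.8 SD | 43% | 14% |

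**For scale.** To exclude a benefit of size M with 80% probability when the true difference is zero, unadjusted, n per arm = 2 × (1.96 + 0.84)²/M². This gives about 63 for M = 0.5 SD and 25 for M = 0.8 SD.

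**The case against.** **The section is a narrative, not a rigid rule.** It introduces its list as several possible outcomes, and outcome 1 begins tentatively. That is fair as to tone. The tentative verb, however, belongs to the sentence on nonspecific effects; the sentence that follows, on benefit, has no hedge. Outcome 2 strengthens its own verb.

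**Outcome 2 already doubts the null.** It does, but the doubt concerns the instruments rather than the sample size, and it arises only when neither group improves. The null the plan thinks likelier carries no caveat.

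**The outcomes are global, and the figures above are for one endpoint.** This is the strongest point. If no difference means none on any of several measures, a broad real effect would be missed less often. Assume 15 per arm, unadjusted, 0.5 SD on every endpoint and between-endpoint correlation 0.3 to 0.5. All endpoints are then non-significant in roughly 18% to 51% of trials, going from 10 endpoints down to 3. The rate falls but stays material, and it does not fall if the benefit is confined to one measure. The document does not say which reading applies. Nor are the rates specific to outcome 2, which also requires no improvement in either group.

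**Little turns on it.** Making no recommendation would follow from an inconclusive result too, no stopping decision depends on the sentence, and item 14 says this is not a treatment trial. That limits the harm to what is reported.

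**Other documents may help.** Section 4 lists a separate protocol and a grant application that were not supplied, so this point covers only the text reviewed. A power statement there would not by itself make the inference valid without an interval criterion.

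**Conclusion.** The concern holds. As written, the section would report absence of benefit from results that often could not show it. How often depends on inputs the document does not give.

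For a true 0.5 SD effect on a single endpoint, 42% or more are missed under every variant tabulated, even with no dropout and strong baseline adjustment. For 0.8 SD at 15 per arm the range is 16% to 44%, so detection is then the likelier result. The discrepancy in expected losses does not alter the conclusion. The wording should be corrected before the data are examined; the design need not change.

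**What to change.** In outcomes 1 and 2, replace the sentences that conclude no specific benefit with:

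> The MBLT–SPLT difference will be reported with its 95% CI. We will conclude that there is no worthwhile specific benefit only if the CI excludes the minimum important difference in favour of MBLT, fixed in advance; otherwise the result will be reported as inconclusive.

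The sponsor should choose the outcome to which this reading applies and fix its minimum important difference before looking at the data. The statement in outcome 1 that no recommendation would be made, and the caveat in outcome 2 about the assessments, can both stay.

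**Cost.** No extra participants, visits or measurements. Choosing an outcome and a margin is a substantive decision, because the document contains neither. If the change counts as major, approval comes first: item 7 says the Human Research Protection Office "must approve any major amendment to this study prior to its implementation".

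**Downside.** Most nulls could no longer be reported as definite negatives. At 15 per arm, with a true difference of zero and a 0.5 SD margin, only about 25% of null results unadjusted (100 − 75) and 45% adjusted (100 − 55) would qualify.

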**FORM: Application for Human Research**

NUMBER	FORM DATE	PAGE
F200	02/2014	6 of 39

65% of patients with mTBI complaining of insomnia (Beatar, Guilmette, & Sparadeo, 1996; Dikmen, McLean, & Temkin, 1986). Sleep problems in these patients are associated with poorer outcome (Franckeviciute, Varzaityte, & Kimtys, 2008), while resolution of the sleep disturbance is associated with improvement in cognitive functioning (Makley et al., 2009). A recent study demonstrated that sleep disturbances, including reduced sleep efficiency, longer sleep onset latency and shorter REM onset latency, were more persistent in mTBI patients for nearly three years after the injury (Williams et al., 2008), and others have found similar long lasting sleep disruption in these patients (Schreiber et al., 2008). Additionally, sleep complaints have been correlated with increased likelihood of mood disturbance and headaches in post-concussive patients (Chaput, Giguere, Chauny, Denis, & Lavigne, 2009). It has been suggested that mTBI might produce alterations of the normal circadian rhythm, leading to delayed sleep phase syndrome and irregular sleep-wake patterns (Ayalon, Borodkin, Dishon, Kanety, & Dagan, 2007). Of mTBI patients with complaints of insomnia, 36% were recently found to have circadian rhythm sleep disorders that emerged following the brain injury (Ayalon et al., 2007). Moreover, the important relationship between sleep and recovery in patients with brain injuries was highlighted in a recent study that showed that sleep efficiency was correlated with the resolution of post-traumatic amnesia in patients with closed head injuries (Makley et al., 2009). Thus, there is little doubt that mTBI is associated with significant disruption of normal sleep patterns and that poorer sleep is associated with poorer recovery, while improvement in sleep problems is associated with improvement in cognitive functioning.

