**FORM: Application for Human Research**

NUMBER	FORM DATE	PAGE
F200	02/2014	9 of 39

laboratory and provide excellent resolution for evaluating functional changes within the target regions of the anterior cingulate gyrus, hippocampus, and prefrontal cortex. Furthermore, the proposed project will directly assess sleep functioning using actigraphy and correlate these changes in sleep with pre-to post-treatment changes in neurocognitive performance and symptom presentation, as well as functional activity changes.

Briefly, individuals who have experienced a mTBI, with or without loss of consciousness, as verified by a medical report, and who complain of sleep disturbance, will undergo an initial psychological assessment, and will be then fitted with an actigraph to wear for the duration of the study in order to measure baseline sleep as well as any changes in sleep patterns. Individuals will then return to complete two comprehensive neurobehavioral assessment and neuroimaging sessions (functional MRI, structural MRI/diffusion tensor imaging; DTI) separated by 6 weeks. During the intervening 6 weeks, participants will be randomly assigned to receive 30 minutes of morning blue light therapy (MBLT) or a sham placebo amber light treatment (SPLT) daily. Sleep quality and quantity will be measured via continuous wrist actigraphy monitors and self-report inventories.

For interested subjects participating in the last phase of recruitment, we will continue collecting wrist actigraphy and self-report data for an additional 6 weeks after completion of the baseline period and light therapy as an optional part of the study. It is hypothesized that MBLT will improve sleep quality and quantity relative to SPLT, and these improvements will be associated with changes in brain function, brain structure, and reduced post-concussion symptom severity at follow-up assessment.

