**Inclusion criteria:**

- Age range between 18 and 50.
- The primary language of the subjects must be English.
- Subjects have experienced a “concussion” or mTBI within the preceding 18 months, but no sooner than 4 weeks prior to their screening. The occurrence of a concussion or mTBI must be documented by a medical report or other professional witness documentation.
- If documented, Glasgow Coma Scale in the range of 13-15 following the injury.
- At least half of subjects must have evidence of sleep onset insomnia or delayed sleep phase disorder.

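### The planned regression on sleep and mood cannot show which of them caused a blue-light benefit; it should be arm-adjusted and reported as exploratory association

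*Combined protocol and SAP*

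**What the plan says.** I. Biostatistical Analysis lists possible trial results and how each will be read. Under outcome 3, where MBLT outperforms SPLT, it states that regressing change in symptoms or cognition on sleep and mood data "would identify whether this was due to sleep related changes or whether the changes were due to the mood altering effects of MBLT"; it also allows for a combination of the two. The Background (Section 3) shows that for sleep this means change against change: the project will "correlate these changes in sleep with pre-to post-treatment changes in neurocognitive performance and symptom presentation". For mood, outcome 3 says only that measures will be used.

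Four other places bear on the claim:

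- Outcome 2 of the same section: "continued improvement between the two sessions would be expected due to gradual recovery during the first year and due to practice effects".
- Inclusion criteria: the injury must have occurred "within the preceding 18 months, but no sooner than 4 weeks prior to their screening".
- Background: "sleep complaints have been correlated with increased likelihood of mood disturbance and headaches in post-concussive patients".
- Personality and Psychodiagnostic Assessment: the mood and sleep questionnaires are given at the baseline and post-treatment sessions, the same sessions as the symptom and cognitive outcomes. Sleep is also followed between them by actigraphy and daily diary, and staff "collect a weekly Epworth Sleepiness Scale".

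The only covariates named anywhere are light exposures (Six-Week Light Exposure Treatment; Actigraphic Sleep Measurement).

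**The concern.** The sentence gives a regression coefficient a causal reading. Randomisation makes the arms comparable, but it does not make people whose sleep improved comparable with people whose sleep did not. Two things can link sleep change to symptom change when sleep has no effect on symptoms:

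1. Light may shift both by separate routes. Pooling the arms without an arm term then produces a correlation.
2. Someone recovering faster may sleep better, feel better and report fewer symptoms over the same six weeks. An arm term does not remove this.

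The second route needs recovery that varies between people. The eligibility window makes that likely: some participants will be inside the first year, in which the plan expects gradual recovery, and some beyond it.

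Sleep as the route to recovery is the study's central hypothesis. A false attribution would misdirect follow-on work even if the efficacy result were correct.

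**Working it through.** **Inputs from the documents.** Study Population aims for 30 complete datasets, and Six-Week Light Exposure Treatment assigns half to each light: 30/2 = 15 per arm. No alpha, SD, effect size or expected slope is given for this regression, so there is no plan figure to reproduce.

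**Assumptions.** Two-sided 0.05. Changes are normal with within-arm SD 1, and each of sleep, mood and symptoms follows: change = 0.8·T + √ρ·U + √(1−ρ)·e. Here T is arm (0 or 1), U is a person's own recovery and e is independent noise. The within-arm correlation between any two changes is then ρ, varied from 0 to 0.5. Neither sleep nor mood affects symptoms.

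**Step 1: sleep only, no arm term.** With half in each arm, the arm difference adds 0.8²/4 = 0.16 to each variance and each covariance. The pooled correlation is (ρ + 0.16)/1.16. At n = 30 a correlation is significant beyond about tanh(1.96/√27) = 0.36. The rates below are from simulation, restricted to trials with a significant MBLT benefit, since only those reach outcome 3. Repeated runs differ by one or two points.

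| ρ | pooled r | sleep falsely significant |
|---|---|---|
| 0 | 0.16/1.16 = 0.14 | 14–16% |
| 0.1 | 0.26/1.16 = 0.22 | 29% |
| 0.2 | 0.36/1.16 = 0.31 | 48–49% |
| 0.3 | 0.46/1.16 = 0.40 | 68–70% |
| 0.5 | 0.66/1.16 = 0.57 | 96% |

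**Step 2: add an arm term.** In the same trials the rate is 5% at ρ = 0, 34% at 0.3 and 80% at 0.5. The arm term removes the link created by treatment, but not the one created by shared recovery.

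**Step 3: sleep and mood together.** This is closer to the plan's sentence. It covers all simulated trials (4,000 per setting), not only those MBLT wins. The expected false slope for each predictor is ρ/(1 + ρ) with an arm term and (ρ + 0.16)/(1.32 + ρ) without. The simulated means agree to within 0.01.

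| ρ | slope, no arm / arm | sleep significant, no arm / arm | sleep or mood significant, no arm / arm |
|---|---|---|---|
| 0 | 0.12 / 0 | 10% / 5% | 19% / 9% |
| 0.1 | 0.18 / 0.09 | 15% / 8% | 29% / 14% |
| 0.2 | 0.24 / 0.17 | 25% / 13% | 44% / 26% |
| 0.3 | 0.28 / 0.23 | 32% / 21% | 58% / 39% |
| 0.5 | 0.36 / 0.33 | 50% / 42% | 82% / 72% |

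For two independent tests the nominal rate in the last column is 1 − 0.95² = 9.75%. Adjusting for U itself, were it observed, returns the rate to 9–10%.

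**Step 4: can it separate sleep from mood?** Let all benefit run through mood (slope 0.60) and none through sleep. With an arm term, sleep is wrongly significant in 14%, 22% and 41% of trials at ρ = 0.2, 0.3 and 0.5. The mood slope rises to 0.76, 0.83 and 0.93.

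**Step 5: sample size.** At n = 2,000 and ρ = 0.3, with an arm term, the false sleep slope is still 0.23 and is significant in every run. This is bias, not imprecision.

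**The case against.** Several points on the other side stand:

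- **The branch.** The attribution is made only if MBLT wins. With no treatment effect, the sleep-only regression is significant in 37–83% of trials at ρ = 0.3–0.5, and a reader might infer that false proof of the sleep mechanism would be reported in most null trials. The documents do not support that. Outcomes 1 and 2 would apply, and a significant regression together with an MBLT win occurs in only about 1–2% of such trials.
- **Recovery common to everyone.** A reader might infer that expected recovery alone makes the changes correlate. A uniform shift goes into the intercept and leaves the error rate nominal. Only recovery that varies between people does harm. The 4-week to 18-month window makes this plausible, but the documents do not quantify it.
- **Silence.** A reader might infer that the plan excludes an arm term or baseline adjustment. It does not: the section gives interpretations rather than a model, and the attachment list names a separate Protocol and a grant application that were not supplied. The accurate statement is that none of these terms is specified in the text available.
- **Joint entry.** Entering sleep and mood together lowers the false-positive rate for sleep, as Step 3 shows, though not to nominal when ρ exceeds 0.
- **Role.** The regression explains a result and does not decide efficacy.

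None of this rescues the sentence. Within the branch where it applies, it assigns cause to non-randomised variables, and no named covariate addresses recovery.

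**Conclusion.** The claim in outcome 3 does not hold. The regression can show that sleep or mood change goes along with symptom change; it cannot show which one the benefit was due to.

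The size depends on assumptions. With 0.8 SD effects of light and 15 per arm, false attribution to sleep after an MBLT win, in a sleep-only model without an arm term, ranges from about 14% at ρ = 0 to about 96% at ρ = 0.5. At ρ of 0.1 to 0.2 it is 29% to 49%. Both ρ and the 0.8 SD are assumed. That the claim fails does not depend on the exact values.

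The fault is confined to attribution. A reader might infer that the efficacy result is compromised; it is not, because MBLT versus SPLT is a randomised contrast and does not use this regression.

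**What to change.** 1. In outcome 3, replace the claim to identify the cause with wording that calls the analysis exploratory and its results associations.
2. Specify the model: change in the outcome on sleep and mood, with treatment arm, baseline outcome, baseline sleep, baseline mood and time since injury. That is seven predictors for 30 people, leaving 30 − 8 = 22 residual degrees of freedom, so use fewer covariates or fit separate sleep and mood models, chosen in advance.
3. Report estimates with confidence intervals, and a sensitivity analysis for unmeasured confounding between the mediator and the outcome.
4. Early actigraphy or the weekly Epworth may serve as a sleep measure taken before the outcome. State that this does not remove shared recovery, and that mood cannot be time-ordered from the baseline and post-treatment questionnaires.

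The adjustment is partial. If time since injury captured half the variance of the recovery factor (an assumption), the remaining correlation would be 0.5ρ/(1 − 0.5ρ): 0.15/0.85 = 0.18 at ρ = 0.3 and 0.25/0.75 = 0.33 at ρ = 0.5. In a model with arm, baseline values, time since injury and an early sleep measure, false significance is then 14–40% over that range, against 32–78% if time since injury captured none. This is why the rewording in item 1 is the essential change.

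The cost is a wording change, a little more analysis and a weaker mechanistic claim. The trial already plans to collect all the data needed.
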